6.6.2. Pharmacokinetic Statistical Methodology

Pharmacokinetic parameter estimates will be listed and summarized using descriptive statistics, which will be presented separately by body weight category, age category, body surface area, glomerular filtration rate, and region (if applicable).

For log-normal data (eg, the PK parameters: AUCs and C_{\max}), the geometric mean and the corresponding 95% CI, and geometric CV% will also be presented.

Additional analysis may be performed if warranted upon review of the data.

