
Primary To assess the single-dose pharmacokinetics of lasmiditan in pediatric migraine patients
	
Pharmacokinetic parameters including:
 
 • Maximum observed drug concentration (C_{\max}) • Time to reach C_{\max} (t_{\max}) • Area under the concentration-versus-time curve (AUC) from time zero to infinity ($AUC_{[0-\infty]}$) • AUC from time zero to the time t, where t is the last time point with measurable concentration ($AUC_{[0-t_{\text{last}}]}$)

Secondary To assess the safety and tolerability of a single dose of lasmiditan in pediatric migraine patients
	
Summary of:
 
 • SAEs • AEs • ECG • Vital signs

Exploratory To assess the safety, tolerability, and pharmacokinetics of lasmiditan in Japanese pediatric migraine patients
	
Pharmacokinetic parameters including:
 
 • C_{\max} • t_{\max} • $AUC_{[0-\infty]}$ • $AUC_{[0-t_{\text{last}}]}$ 
Summary of adverse events, SAEs, ECG, and vital signs.

Abbreviations: AE = adverse event; ECG = electrocardiogram; SAE = serious adverse event.

5. Study Design

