5.1. Summary of Study Design

This is a Phase 1, multi-center, open-label, single dose study to determine the pharmacokinetic (PK), safety, and tolerability of lasmiditan in pediatric patients with a diagnosis of migraine.

Two cohorts will be evaluated:

- Primary **Cohort 1**: 15 kg to ≤ 40 kg
- Secondary **Cohort 2**: >40 kg to ≤ 55 kg

The planned doses for Cohorts 1 and 2 are 100 mg and 200 mg, respectively.

Study Period I (Screening)

All patients are screened to determine if they are eligible to participate in the study.

Screening will occur 28 days to 3 days prior to lasmiditan dosing.

Study Period II (PK Assessment/Safety)

Enrolled patients and the patient's parent or guardian will receive instructions regarding study procedures prior to dosing, including fasting requirements.

Day 1:

- Patients arrive at the Clinical Research Unit (CRU) for assessments prior to dosing.
- Patients receive the single lasmiditan dose.
- Patients can go home after the 12-hour assessments. Patients may be offered the opportunity to spend the night depending on CRU capabilities.

Day 2:

- Patient assessments are done at the CRU approximately 24 hours after dosing.

Study Period III (Follow-Up Period)

Patients return to the CRU for a follow-up visit approximately 14 days after dosing.

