Safety analyses will be conducted for all enrolled patients who receive a dose of the investigational product, whether or not they completed all protocol requirements.

Pharmacokinetic data analyses will be presented by:

- body weight category (15 kg to ≤ 40 kg, >40 kg to ≤ 55 kg)
- age category (6 to <12 years of age, 12 to <18 years of age)
- body surface area (0.65 m² to ≤ 1.3 m², >1.3 m² to ≤ 1.6 m²)
- glomerular filtration rate (<75 mL/min/1.73 m², ≥ 75 mL/min/1.73 m²)
- region (Japan, US), if appropriate

Safety data analyses will be presented by body weight category or age category, as appropriate.

All protocol deviations that occur during the study will be considered for their severity/impact and will be taken into consideration when PK and safety analyses are conducted.

Data analysis will be performed using SAS[®] Version 9.4 or greater.

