6.6. Pharmacokinetic Assessment

6.6.1. Pharmacokinetic Analysis

Pharmacokinetic parameter estimates will be determined using non-compartmental procedures in validated software program (Phoenix WinNonlin Version 6.4 or later). Pharmacokinetic analysis using a compartmental modeling approach will be described in a separate PK/pharmacodynamic analysis plan document.

Plasma concentrations of lasmiditan will be used to determine the following PK parameters, when possible:

Parameter	Units	Definition
C_{\max}	ng/mL	maximum observed drug concentration
t_{\max}	h	time of maximum observed drug concentration
AUC(0- ∞)	ng.h/mL	area under the concentration versus time curve from time zero to infinity
AUC(0- t_{last})	ng.h/mL	area under the concentration versus time curve from time zero to time t, where t is the last time point with a measurable concentration
%AUC(t_{last} - ∞)	%	percentage of AUC(0- ∞) extrapolated
$t_{1/2}$	h	half-life associated with the terminal rate constant (λ_z) in non-compartmental analysis
CL/F	L/h	apparent total body clearance of drug calculated after extra-vascular administration
V_z/F	L	apparent volume of distribution during the terminal phase after extra-vascular administration
V_{ss}/F	L	apparent volume of distribution at steady state after extra-vascular administration

Additional PK parameters may be calculated, as appropriate. The software and version used for the final analyses will be specified in the clinical study report. Any exceptions or special handling of data will be clearly documented within the final study report.

Formatting of tables, figures, and abbreviations will follow the Eli Lilly and Company (Lilly) Global PK/PD/TS Tool: NON-COMPARTMENTAL PHARMACOKINETIC STYLE GUIDE. The version of the tool effective at the time of PK analysis will be followed.

General PK Parameter Rules

- Actual sampling times will be used in the final analyses of individual PK parameters, except for non-bolus pre-dose sampling times which will be set to zero. For non-bolus, multiple dose profiles, the pre-dose time will be set to zero unless a time deviation falls outside of the protocol blood collection time window which is considered to impact PK parameter derivation.
- C_{\max} and t_{\max} will be reported from observed values. If C_{\max} occurs at more than 1 time point, t_{\max} will be assigned to the first occurrence of C_{\max} .

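### Cmax and AUC are summarised by age, GFR and region without separating the 100-mg and 200-mg cohorts, so these summaries can partly reflect dose mix

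*SAP*

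**What the plan says.** Dose follows weight category. SAP section 5.1 states: "The planned doses for Cohorts 1 and 2 are 100 mg and 200 mg, respectively". Cohort 1 is 15 to 40 kg, Cohort 2 is above 40 and up to 55 kg, and Table LAHX.5.1 repeats this.

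Section 6.6.2 has the PK parameters summarised and "presented separately by body weight category, age category, body surface area, glomerular filtration rate, and region (if applicable"). For AUC and Cmax, "the geometric mean and the corresponding 95% CI, and geometric CV% will also be presented". Section 6.1 defines the strata, among them "age category (6 to <12 years of age, 12 to <18 years of age") and "region (Japan, US), if appropriate". Nothing crosses age, BSA, GFR or region with cohort or dose, and no count of patients per dose is planned for these strata.

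The parameter list in section 6.6.1 contains CL/F, the "apparent total body clearance of drug calculated after extra-vascular administration", and Vz/F, the "apparent volume of distribution during the terminal phase after extra-vascular administration", together with Vss/F. It names no Cmax/dose or AUC/dose. It allows further parameters where appropriate, without committing to any.

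Table LAHX.4.1 has an exploratory objective: "To assess the safety, tolerability, and pharmacokinetics of lasmiditan in Japanese pediatric migraine patients". Its PK endpoints are Cmax, tmax, AUC(0-∞) and AUC(0-tlast).

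**The concern.** Only the weight-category table is certain to hold one dose per column. In an age, GFR or region stratum that holds both cohorts, the geometric mean of Cmax or AUC depends on the share of patients on 200 mg, and the geometric CV includes the spread between the two dose groups. Age goes with weight and therefore with dose, and nothing in the plan balances dose across regions. With about 11 + 6 evaluable patients, one or two patients can change the mix.

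The stake is interpretation. A difference between two strata, or the absence of one, could be taken for a PK finding when part of it comes from how many patients received each dose. Cmax is the most exposed. It is a primary endpoint and an endpoint of the Japanese objective, and no planned parameter shows it free of dose.

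**Working it through.** **The plan's own figure.** SAP section 5.2 claims at least 80% probability that the 95% CI for the geometric mean lies within 70% to 140%, with 11 patients and CV 45%. Log-scale SD σ = √ln(1 + 0.45²) = 0.429. The half-width t·s/√n must not exceed ln 1.4 = 0.336. With t(0.975, 10) = 2.228, s must be at most 0.336 × √11 / 2.228 = 0.501. Then P[χ²(10) ≤ 10 × (0.501/0.429)²] = 80.8%. With n = 10 the result is 71.0%. The claim is reproduced. It concerns Cohort 1 alone, which receives one dose level, so dose mix does not touch it.

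**Which strata mix doses.** Weight: none. Age, GFR and region: either cohort can fall in either stratum. BSA: the Boyd formula in section 6.5.1 gives 1.258 m² at 40 kg and 135 cm, 1.298 at 150 cm and 1.324 at 160 cm. The PK cut of 1.3 m² in section 6.1 therefore nearly coincides with the 40-kg dose cut, and the BSA strata are largely separated by dose. (Section 6.5.1 uses 1.2 m² for the demographic table. With that cut, patients of 40 kg at these heights would sit in the upper stratum and mixing would be more likely.)

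**Formulas.** R is the 200-mg to 100-mg exposure ratio, and p and q are shares of a stratum on 200 mg.
- Geometric mean ratio from dose mix alone = R^(q₂ − q₁).
- Geometric CV of a mixed stratum = √(exp[ln(1 + CV²) + p(1 − p)(ln R)²] − 1).

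**Inputs.** The within-dose CVs are the adult inter-patient values in section 5.2: 39% for AUC and 43% for Cmax. R is not in the documents. The assumed cases, with the same R used for Cmax and AUC, are:
- R = 1: weight-tiered dosing matches exposure exactly.
- R = 2 × (28/47)^b, for exposure falling with weight to the power b and assumed typical weights of 28 and 47 kg: 1.36 for b = 0.75, 1.19 for b = 1.
- R = 2: dose-proportional PK and clearance independent of weight. This is the upper bound considered.

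**Result for a stratum half on 200 mg against one all on 100 mg** (q₂ − q₁ = 0.5, so the ratio is √R; 60% against 10% gives the same ratio):

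| R | Geometric mean ratio | AUC CV, from 39% | Cmax CV, from 43% |
|---|---|---|---|
| 1.00 | 1.00 | 39% | 43% |
| 1.19 | 1.09 | 40% | 44% |
| 1.36 | 1.16 | 42% | 46% |
| 2.00 | 1.41 | 55% | 58% |

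(The ratio 1.16 uses R = 1.356; rounding R to 1.36 first gives 1.17.) For R = 2 and AUC: ln(1 + 0.39²) = 0.1416; 0.25 × (ln 2)² = 0.1201; √(exp(0.2617) − 1) = 54.7%.

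**What dividing by dose does.** It replaces R by R/2. At 28 and 47 kg this gives 0.68 (b = 0.75) or 0.60 (b = 1), further from 1 on the log scale than 1.36 or 1.19. The half-mixed CV becomes 44% to 48% for AUC and 48% to 52% for Cmax, above the raw 40% to 42% and 44% to 46%. Next to the cut it helps: for 39 and 41 kg the raw ratio is 2 × (39/41)^b = 1.93 or 1.90, and the normalised ratio is 0.96 or 0.95.

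**The case against.** The strongest reply is that exposure under the weight-tiered regimen is itself a legitimate quantity. The protocol addendum (section 4.6) uses the same 40-kg cut and the same 1:2 dose ratio to aim at one adult-equivalent exposure. If R is near 1, dose mix adds nothing. Dose-normalised values remove the dose step but leave the weight effect that tiering offsets, and the calculation confirms that they can look worse than the raw ones. This stands as an argument against relying on dose-normalised values alone. It does not settle R, because the addendum's target is stated for other doses, and in this study R is unknown.

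Three further replies stand in part.
- CL/F is dose divided by AUC(0-∞) and is summarised by the same strata. A reader might infer that the plan contains no dose-adjusted parameter; that is not so. The gap is Cmax, and AUC(0-tlast) directly.
- A reader might infer that a Japan-US comparison is a stated objective. Table LAHX.4.1 speaks only of assessing Japanese patients, and the region tables are conditional.
- Listings are by cohort and dosing is listed per patient (sections 6.1 and 6.3), so a reader could rebuild the dose split by hand. That is possible with so few patients, but the summary tables would not show it.

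Pooling is inferred from silence. The inference is reasonable, since section 6.7.5 asks for vital-sign figures by both cohort and region and section 6.6.2 asks for nothing similar. The main LAHX protocol and the separate PK/pharmacodynamic analysis plan were not supplied and may say more.

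**Conclusion.** The point holds as a limited reporting gap of low severity. Followed as written, the age, GFR and region summaries of Cmax and AUC can mix two doses with nothing in the table to show it. A BSA contrast can hardly be told apart from a dose and weight contrast.

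The size rests on R. Under the assumed weight scaling it is modest: a geometric mean ratio of 1.09 to 1.16, and CVs one to three percentage points higher. The figures 1.41, 55% and 58% are tempting as the expected effect, but they need clearance to be independent of weight from 15 to 55 kg, which the documents do not support. They are an upper bound. Nor can it be said that the CVs will be inflated, because at R = 1 they are not.

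The analyses are descriptive. The weight-category summary and the 11-patient precision statement are unaffected.

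**What to change.** In SAP section 6.6.2:
- Show the number of patients per dose in each age, BSA, GFR and region stratum.
- Present Cmax and AUC by age, GFR and region within dose cohort, or add Cmax/dose and AUC/dose beside the un-normalised values. Keep the un-normalised values as the description of exposure under the regimen.
- Name CL/F as the parameter for comparing AUC between subgroups.

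The cost is a few rows in existing descriptive tables; no sample-size figure changes. Splitting by cohort leaves small cells, as Cohort 2 aims for only 6 evaluable patients. Dose-normalised values assume dose proportionality between 100 and 200 mg and still carry the body-weight effect, so they should be read with the per-dose counts and not alone.

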6.7. Safety and Tolerability Assessments

6.7.1. Adverse Events

Where changes in severity are recorded in the Case Report Form (CRF), each separate severity of the AE will be reported in the listings, only the most severe will be used in the summary tables. A pre-existing condition is defined as an AE that starts before the patient has provided written informed consent and is ongoing at consent. A treatment-emergent AE (TEAE) is defined as an AE which occurs postdose or which is present prior to dosing and becomes more severe postdose. A non-treatment emergent AE (non-TEAE) is defined as an AE which starts after informed consent but prior to dosing.

All AEs occurring on or after the date of informed consent form signing, discontinuations due to AEs, pre-existing conditions and medical history, serious AEs, and serious TEAEs will be listed.

The number and percentage of patients who report TEAEs will be summarized using preferred terms (PTs) from the most current version of Medical Dictionary for Regulatory Activities (MedDRA), where PTs will be nested within system organ class (SOC). System organ classes will be listed alphabetically and PTs within each SOC will be listed by decreasing frequency in the total population. The number and percentage of patients who report TEAEs will also be summarized using MedDRA PTs listed by decreasing frequency in the total population.

The number and percentage of patients with TEAEs by maximum severity will be summarized using MedDRA PTs listed by decreasing frequency in the total population. For each patient and TEAE, the maximum severity for the MedDRA PT is the maximum post-baseline severity observed from all associated lower level terms mapping to the MedDRA PT. The maximum severity will be determined based on the non-missing severities. If all severities are missing for the defined postbaseline period of interest, it will show as missing in the table.

The number and percentage of patients with TEAEs that are related to study drug will be summarized using MedDRA PTs listed by decreasing frequency in the total population. Related TEAEs are those that are recorded on the AE CRF page as related to study treatment or those with a missing relationship.

For events that are gender-specific, the denominator and computation of the percentage will include only patients from the specific gender.

Descriptive statistics will be presented separately by body weight category and age category.

6.7.2. Concomitant Therapy

Concomitant medications taken during the study will be coded using the most current version of the World Health Organization drug dictionary. All concomitant medications will be listed.

6.7.3. Prior Migraine Therapy

All migraine therapies that patients have stopped taking prior to the date of informed consent signing will be provided in a listing.

6.7.4. Clinical Laboratory Evaluation

6.7.4.1. Clinical Laboratory Parameters

All clinical chemistry, hematology, and urinalysis data will be summarized by parameter, and listed. Values for any clinical chemistry, hematology, and urinalysis that are outside the reference ranges will be flagged as high or low on the individual patient data listings.

Change from baseline will be summarized for all lab parameters measured at 24 hours postdose, where baseline is defined as the predose measurement for all laboratory parameters.

6.7.4.2. Hepatic Monitoring

Patients with the following elevations in hepatic laboratory tests at 24 hours postdose will be listed:

- Patients with an alanine aminotransferase (ALT) measurement greater than or equal to 3X, 5X, and 10X the performing laboratory upper limit of normal (ULN) at 24 hours postdose will be listed by the following subsets based on various levels of baseline value.
 - The analysis of 3X ULN will contain 4 subsets:
 - patients whose non-missing baseline ALT value is less than or equal to 1X ULN
 - patients whose baseline ALT value is greater than 1X ULN but less than 3X ULN
 - patients whose baseline ALT value is greater than or equal 3X ULN
 - patients whose baseline ALT values are missing

- The analysis of 5X ULN will contain 5 subsets:
 - patients whose non-missing baseline ALT value is less than or equal to 1X ULN
 - patients whose baseline ALT value is greater than 1X ULN but less than 3X ULN
 - patients whose baseline ALT value is greater than or equal to 3X ULN but less than 5X ULN
 - patients whose baseline ALT value is greater than or equal to 5X ULN
 - patients whose baseline ALT values are missing
- The analysis of 10X ULN will contain 6 subsets:
 - patients whose non-missing baseline ALT value is less than or equal to 1X ULN
 - patients whose baseline ALT value is greater than 1X ULN but less than 3X ULN
 - patients whose baseline ALT value is greater than or equal to 3X ULN but less than 5X ULN
 - patients whose baseline ALT value is greater than or equal to 5X ULN but less than 10X ULN
 - patients whose baseline ALT value is greater than or equal to 10X ULN
 - patients whose baseline ALT values are missing
- Patients with an aspartate aminotransferase (AST) measurement greater than or equal to 3X, 5X, and 10X the performing lab ULN at 24 hours post-dose will be listed by subsets based on various levels of baseline value, as described above for ALT.
- Patients with an alkaline phosphatase (ALP) measurement greater than or equal to 2X the performing lab ULN at 24 hours post-dose will be listed by the following subsets based on various levels of baseline.
 - The analysis of 2X ULN will contain 4 subsets:
 - patients whose non-missing baseline ALP value is less than or equal to 1X ULN
 - patients whose baseline ALP value is greater than 1X ULN but less than 1.5X ULN
 - patients whose baseline ALP value is greater than or equal to 1.5X ULN

- patients whose baseline ALP values are missing
- Patients with a total bilirubin (TBIL) measurement greater than or equal to 2X the performing lab ULN at 24 hours postdose will be listed by the following subsets based on various levels of baseline:
 - patients whose non-missing baseline TBIL value is less than or equal to 1X ULN
 - patients whose baseline TBIL value is greater than 1X ULN but less than 2X ULN
 - patients whose baseline TBIL value is greater than or equal to 2X ULN
 - patients whose baseline TBIL values are missing

Baseline is defined as the predose measurement for all hepatic laboratory parameters.

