4.11. Discontinuation of Study Treatment

Possible reasons leading to discontinuation of lasmiditan:

- Pregnancy
- The participant or the participant's parents or legal guardian requests to discontinue lasmiditan
- A hepatic event or liver test abnormality

Discontinuation of the investigational product for abnormal liver tests **should be considered** by the investigator when a patient meets 1 of the following conditions after consultation with the Lilly-designated medical monitor:

- alanine aminotransferase (ALT) or aspartate aminotransferase (AST) >8x upper limit of normal (ULN)
- ALT or AST >5x ULN sustained for more than 2 weeks
- ALT or AST >3x ULN and total bilirubin level (TBL) >2x ULN or international normalized ratio >1.5
- ALT or AST >3x ULN with the appearance of fatigue, nausea, vomiting, right upper-quadrant pain or tenderness, fever, rash, and/or eosinophilia (>5%)
- alkaline phosphatase (ALP) >3x ULN
- ALP >2.5x ULN and TBL >2x ULN
- ALP >2.5x ULN with the appearance of fatigue, nausea, vomiting, right quadrant pain or tenderness, fever, rash, and/or eosinophilia (>5%).

Participants who are discontinued from investigational product due to a hepatic event or liver test abnormality should have additional hepatic safety data collected via eCRF.

- Participants experiencing signs of suicidal ideation or behavior
Discontinuation of investigational product should be considered, following a risk assessment, for participants who
 - answered “yes” to Question 4 or Question 5 on the “Suicidal Ideation” portion of the Columbia-Suicide Severity Rating Scale (C-SSRS), **or**

- answered “yes” to any of the suicide-related behaviors on the Suicidal Behavior portion of the C-SSRS.

A psychiatrist or appropriately trained professional may assist in the decision to discontinue the participant.

Participants discontinuing from the investigational product prematurely for any reason should complete AE and other follow-up procedures per [Attachment 1](#) (Schedule of Activities) of the addendum, and Section 8.2 (Safety Assessments) and Section 8.3 (Adverse Events and Serious Adverse Events) of the protocol.

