Attachment 1. Schedule of Activities

Schedule of Activities for Patients Participating in H8H-MC-LAHX(1) Addendum

Visit		Month 1	Month 2	Month 3 EOS	ED	Notes
	4 ^a	5	6	7		
(Target) interval (days) since previous visit		30±3	30±3	30±3		
Procedure/Assessments						
Informed consent/assent	X					Consent and assent form signed by patient and parent or guardian.
Physical examination	X	X	X	X	X	
Vital signs	X	X	X	X	X	Blood pressure, pulse, and temperature. Triplicate measurements at all visits, in the sitting position. Measure blood pressure by an automated calibrated machine, if calibration is required
Weight	X					
Menstrual status	X	X	X	X		
12-lead ECG (single)	X			X	X	Patients must be supine for at least 5 minutes before collection and remain supine, but awake during the procedure
Concomitant medications	X	X	X	X	X	
Adverse events	X	X	X	X	X	
Study drug dispensed	X	X	X			Provide detailed instructions to participant for study drug
Review study diary	X	X	X	X	X	
Study drug accountability		X	X	X	X	Collect empty dosing card(s) and unused study drug. Review dosing compliance
Clinical Laboratory Tests						
Hematology	X			X	X	
Clinical chemistry	X			X	X	
Urinalysis	X			X	X	
Urine drug screen	X	X	X	X	X	For patients aged ≥ 10 years
Pregnancy test for females of childbearing potential	X	X	X	X	X	A positive urine pregnancy test must be followed by a serum pregnancy test for confirmation
Scales and Questionnaires						
C-SSRS/SHSF/SHFU	X	X	X	X	X	Suicidal ideation and behavior subscales are adapted for the assessment of 11 preferred ideation and behavior categories. The C-SSRS will be collected only in patients ≥7 years old. The SHFU Form is required only if triggered by the SHSF
PGI-C		X	X	X	X	The PGI-C is contained within the patient diary

Abbreviations: C-SSRS = Columbia-Suicide Severity Rating Scale; ECG = electrocardiogram; ED = early discontinuation; EOS = end of study visit; PGI-C = Patient Global Impression of Change; SHFU = Self-Harm Follow-Up form; SHSF = Self-Harm Supplement Form.

^a The confirmation of eligibility visit for the addendum will occur at the same time as Study LAHX Day 14, Follow-up visit.

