Attachment 2. Clinical Laboratory Tests

Hematology^a

Hemoglobin
 Hematocrit
 Erythrocyte count (RBC)
 Mean cell volume
 Mean cell hemoglobin
 Mean cell hemoglobin concentration
 Leukocytes (WBC)
 Platelets

Absolute counts of:

Neutrophils
 Lymphocytes
 Monocytes
 Eosinophils
 Basophils

Urinalysis^a

Specific gravity
 pH
 Protein
 Glucose
 Ketones
 Bilirubin
 Urobilinogen
 Leukocyte esterase^b
 Blood
 Nitrite
 Urine culture^b
 Microscopic analysis^b

Clinical Chemistry^a

Sodium
 Potassium
 Bicarbonate
 Chloride
 Calcium
 Phosphorus
 Magnesium

 Total bilirubin

 Direct bilirubin
 Alkaline phosphatase (ALP)
 Aspartate aminotransferase (AST)
 Alanine aminotransferase (ALT)
 Blood urea nitrogen (BUN)
 Creatinine
 Uric acid

 Glucose (random)
 Albumin
 Total protein

Other Tests

Serum pregnancy test^a
 Urine pregnancy test (local)

 Urine drug screen^a

Abbreviations: RBC = red blood cell; WBC = white blood cell.

^a Assayed by sponsor-designated laboratory.

^b A positive leukocyte esterase result will require a follow-up sample with microscopic analysis and possibly a urine culture.

Note: Additional tests may be performed at the discretion of the investigator as needed.

Protocol H8H-MC-LAHX Addendum Sampling Summary

Purpose	Blood Volume per Sample (mL)	Maximum Number of Blood Samples	Total Volume (mL)
Hematology ^a	2	2	4
Chemistry ^a	2.5	2	5
Serum pregnancy test ^{a,b}	0	1	0
Total			9
Total for clinical purposes rounded up to the nearest 10 mL			10
Hepatic monitoring ^c			3-30

Abbreviations: CRP = Clinical Research Physician; CRS = Clinical Research Scientist.

^a Additional samples may be drawn if needed for safety purposes.

^b Sample volume included with chemistry test volume.

^c Unscheduled hepatic monitoring testing may be performed as part of patient follow-up, based on laboratory safety values and in consultation with Lilly CRP/CRS.

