6.2. Handling of Dropouts or Missing Data

Missing data will not be displayed in listings.

Some of the tables, figures, and listings (TFLs) may not have sufficient numbers of patients or data for presentation. If this occurs, the blank TFL shell will be presented with a message printed in the center of the table, such as, “No serious adverse events occurred for this study”.

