Diastolic BP (mm Hg) (orthostatic)	All	Decrease	Decrease ≥ 10	All patients

Abbreviations: BP = blood pressure; bpm = beats per minute; mm Hg = millimeters of mercury.

Note: "all patients" include all safety analysis patients with both a non-missing baseline (predose) measure and at least 1 non-missing postbaseline measure.

Beasley and Moscarelli 2015.

The criteria consist of 2 parts, an absolute threshold and a change from baseline (predose) amount.

- The absolute threshold in the criteria is based on: 1) minimum postbaseline when the direction is low; 2) maximum postbaseline when the direction is high.
- The change from baseline amount in the criteria is: 1) decrease from non-missing baseline to minimum postbaseline when the direction is low; 2) increase from non-missing baseline to maximum post baseline when the direction is high.

6.7.6. *Electrocardiograms*

Any clinically significant electrocardiogram (ECG) finding that results in a diagnosis and that occurs after the patient receives lasmiditan will be reported as an AE.

Counts and percentages displaying shifts from normal, abnormal (not clinically significant), or abnormal (clinically significant) at baseline (predose) to normal, abnormal (not clinically significant), or abnormal (clinically significant) at 24 hours postdose will be summarized. Baseline is defined as ECG findings taken at predose.

Descriptive statistics will be presented separately by body weight category and age category.

6.7.7. *Cognition*

Data for the following Cogstate Pediatric Brief Battery parameters will be listed by time point:

- Detection Test score: mean of the \log_{10} transformed reaction times for correct responses
- Identification Test score: mean of the \log_{10} transformed reaction times for correct responses
- One Back Test score: mean of the \log_{10} transformed reaction times for correct responses
- One Card Learning Test score: arcsine transformation of the square root of the proportion of correct responses

For each test score, listings will also include change from baseline (predose) and the reliable change index (RCI) score at each post-dose time point, which will be computed as follows:

$$RCI = \frac{score_{post} - score_{baseline}}{s_{norm}\sqrt{2(1-r)}} \times Multiplicand$$

where:

- $score_{post}$ = patient's score at the given post-dose time point
- $score_{baseline}$ = patient's score at baseline
- s_{norm} = population standard deviation from age-matched normative data

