6.7.8.2. Evaluation of Hepatic Safety

Refer to Section 6.7.4.2 for a description of hepatic analyses.

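### The SAP grades liver tests by ULN multiple only at 24 hours postdose, so a later postdose elevation would be listed and flagged high but left out of the hepatic listings (minor)

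*SAP*

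**What the plan says.** SAP 6.7.4.2 (Hepatic Monitoring) begins: "Patients with the following elevations in hepatic laboratory tests at 24 hours postdose will be listed". It repeats the 24-hour time point for each analyte: ALT and AST at 3X, 5X and 10X ULN, and ALP and total bilirubin at 2X ULN. Each listing is split by the child's predose value. The section has no rule for later or unscheduled results.

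Hepatic safety is one of the SAP's safety topics of interest, but SAP 6.7.8.2 contains only a pointer: "Refer to Section 6.7.4.2 for a description of hepatic analyses". The cardiovascular and hypersensitivity topics (6.7.8.1 and 6.7.8.7) have a MedDRA search; the hepatic topic has none. The listings in 6.7.4.2 are therefore all of the planned hepatic evaluation.

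SAP 6.7.4.1 is wider. All chemistry data are to be summarized and listed, with no time limit stated, and values outside the reference range "will be flagged as high or low on the individual patient data listings". Its change-from-baseline summary is at 24 hours.

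On later samples, the schedule in Protocol addendum Attachment 1 marks clinical chemistry at Visit 4, and footnote a says: "The confirmation of eligibility visit for the addendum will occur at the same time as Study LAHX Day 14, Follow-up visit". The panel in Attachment 2 includes ALT, AST, ALP and bilirubin. Note c to the addendum sampling summary there adds: "Unscheduled hepatic monitoring testing may be performed as part of patient follow-up, based on laboratory safety values".

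**The concern.** A reader who wants to know whether any child reached 3X ULN after lasmiditan will go to the hepatic section. As worded, that section answers only for the sample taken about a day after the dose. A child whose ALT is normal at 24 hours and raised two weeks later meets none of the listing criteria, even though the later value may be in the database.

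The general laboratory listing does not fully replace the grading. Its flag has two levels, high and low, so 1.1X ULN and 8X ULN are marked alike, and the baseline subset is not shown.

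Two other parts of the documents look beyond a single early sample. The blood pressure and pulse criteria in SAP 6.7.5 use the "maximum postbaseline when the direction is high", and the corresponding minimum for low values. The addendum's liver criteria in Protocol 4.11 include "ALT or AST >5x ULN sustained for more than 2 weeks", a pattern that one 24-hour sample cannot show. That criterion governs stopping in the addendum, not the LAHX listings. It shows only that the sponsor regards a persistent elevation as relevant.

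**Working it through.** No arithmetic applies: the point is a time window, and the plan gives no figure to reproduce. The check sets the sections side by side and follows one hypothetical child through them.

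**Which postdose liver tests do the documents show, and which are graded?**

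| Test after the LAHX dose | Source | Listed and flagged (SAP 6.7.4.1) | Graded by ULN multiple (SAP 6.7.4.2) |
|---|---|---|---|
| 24 hours | SAP 6.7.4.1, 6.7.4.2 | Yes | Yes |
| Visit 4 / LAHX Day 14, US children entering the addendum | Addendum Attachment 1, footnote a | Yes, if reported with LAHX data | No |
| Unscheduled hepatic test before any addendum dose | Addendum Attachment 2, note c | Yes, if reported with LAHX data | No |
| Day 14 chemistry in other LAHX children | Not shown | Unknown | No, if drawn |

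Visit 4 comes after the LAHX dose (100 mg or 200 mg by weight, SAP 5.1) and is the visit at which addendum drug is first dispensed. Its chemistry is thus a postdose sample for the single dose, taken before any addendum dose.

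**One child under the present wording.** Suppose ALT is at or below 1X ULN predose and at 24 hours, and 3X ULN at Visit 4.

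1. The 3X ULN listing in 6.7.4.2 tests the 24-hour value only, so the child is not listed.
2. The evaluation in 6.7.8.2 adds nothing, so the child is absent there too.
3. The change-from-baseline summary in 6.7.4.1 uses the 24-hour value and shows no rise.
4. The 6.7.4.1 listing shows the Visit 4 value with a high flag. If Visit 4 is included in the summary, the maximum required by SAP 6.1 shows the raw value without its ULN multiple.
5. If the investigator reports an adverse event, it appears under SAP 6.7.1.

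**The same child under a maximum-postdose rule.** The 3X ULN value enters the 3X listing in the subset with baseline at or below 1X ULN, shown as a Day 14 sample.

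**What the output would look like otherwise.** If no child qualifies at 24 hours, SAP 6.2 says that "the blank TFL shell will be presented with a message printed in the center of the table". The example message there concerns serious adverse events. The wording for a hepatic listing is not given, so how far it might mislead is unknown.

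**The case against.** The best defence is that 24 hours may be the only postdose chemistry in LAHX. The supplied SAP covers the single-dose study, the main LAHX protocol is not supplied, and SAP 5.1 mentions a follow-up visit at about 14 days without naming any laboratory test. If so, the listings cover everything LAHX itself plans. The evidence for later tests comes from the addendum, whose Visit 4 is an eligibility check where a raised value would be seen by a clinician. This stands as a limit: the gap is documented only for US children entering the addendum and for unscheduled tests.

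The comparison with vital signs is also weaker than it looks. Vital signs are taken at several times and need a rule to reduce them to one value. The ECG shifts in SAP 6.7.6 use 24 hours, as the hepatic listings do. That explains the wording, but does not help a child whose later sample is raised.

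Four stronger readings are tempting, and the documents do not support them.

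- A reader might infer that late elevations would go unreported. SAP 6.7.4.1 lists all chemistry values and flags those out of range. With about 13 + 8 = 21 children planned (SAP 5.2), a 3X ULN value can be found by hand.
- A reader might infer that Day 14 liver tests in every LAHX child are left out. The documents do not show that such tests are drawn outside the addendum.
- A reader might infer that an incidence estimate or its confidence interval would be biased. SAP 6.7.4.2 produces patient listings, not proportions, and SAP 6.7.10 plans no inferential analysis.
- A reader might infer that the end-of-addendum or early-discontinuation liver tests have been wrongly left ungraded. The supplied SAP is for the single-dose study. Protocol 4.16.2.1 defers further PGI-C analyses to a statistical analysis plan, and the supplied SAP has none. The addendum's analyses may therefore be specified in a document not supplied.

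**Conclusion.** The point holds as a minor one. The only planned hepatic evaluation grades liver tests at 24 hours postdose and at no other time. A later postdose elevation would not be grouped by ULN multiple or baseline subset.

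The effect is on how a safety listing reads. It does not touch the pharmacokinetic objective. The rate of later elevations is not in the documents, so no size can be put on the number of children affected, and it may be none.

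The conclusion assumes that Visit 4 chemistry, or an unscheduled test before addendum dosing, is available to the LAHX report. If LAHX has no liver test after 24 hours in any child, the present wording already covers everything.

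**What to change.** In SAP 6.7.4.2, wherever the 24-hour time point appears, use instead the maximum postdose value, scheduled or unscheduled, before any addendum dose. Keep the thresholds, the predose baseline and the baseline subsets. Show the sampling time beside each listed value, so that 24-hour and later results can be told apart. State how many children have a liver test after 24 hours.

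The cost is a change of wording and a selection rule in listings that are already planned, with no added visit or blood draw. There are two downsides. A value two weeks after a single dose is harder to attribute to it than a 24-hour value, which is why the sampling time should be shown. Coverage after 24 hours will be uneven, because the documents confirm Visit 4 chemistry only for US children who enter the addendum and unscheduled tests depend on earlier results. The stated count lets the reader judge how much an empty listing means.
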